### 7.6.1.2 AE Frequency Table

An AE will be considered to have developed during an analysis period if the imputed AE start date is in the analysis period. See Section 7.6.1.1 for AE start date imputation.

Frequency tables will present the number and percentage of subjects experiencing AEs during analysis periods. The following counting rules will apply:

- In AE tables by severity, SOC, and PT, a subject's worst severity of a PT during the analysis period will be reported. A subject will contribute only once to the count for a given AE SOC or PT, regardless of the number of events.
  - Severities may include total (i.e., any severity including missing), mild, moderate, and severe.
  - Example: If subject has 1 mild rash AE and 2 moderate rash AEs, then the subject will be counted under rash once in both the total and moderate severities.
- In AE tables by SOC and PT, a subject will contribute only once to the count for a given AE SOC or PT, regardless of the number of events.
- In AE tables by PT, a subject will contribute only once to the count for a given AE PT, regardless of the number of events.

## 7.6.1.3 Treatment-Emergent AEs

Treatment-emergent AEs (TEAEs) are those that developed, worsened, or became serious during the on-treatment analysis period relative to the pre-treatment analysis period. For a given subject and PT, the following will apply:

- An AE developed on treatment if the first occurrence (as determined by the imputed start date) is on treatment.
- An AE worsened on treatment if the worst on-treatment severity is greater than the worst pre-treatment severity (including not reported).
- An AE became serious on treatment if (1) at least one on-treatment AE has serious status of "yes", and (2) no pre-treatment AE has serious status of "yes".

Thus, TEAEs are a subset of on-treatment AEs.

## 7.6.1.4 AEs of Special Interest

### **Hepatic-Related AEs**

Hepatic-related AE PTs will include the following:

• "Hepatic disorders" SMQ: All PTs except those in "Congenital, familial, neonatal and genetic disorders of the liver" SMQ.

#### Cardiovascular AEs

Cardiovascular AE PTs will include the following:

 "Conditions associated with central nervous system haemorrhages and cerebrovascular accidents" SMQ: Narrow PTs

- "Ischaemic central nervous system vascular conditions" SMQ: Narrow PTs
- "Embolic and thrombotic events, arterial" SMQ: peripheral arterial occlusive disease; peripheral arterial reocclusion; peripheral artery angioplasty; peripheral artery bypass; peripheral artery occlusion; peripheral artery stent insertion; peripheral artery thrombosis
- "Ischaemic colitis" SMQ: Narrow PTs
- "Ischaemic heart disease" SMQ
  - o "Myocardial infarction" SMQ: Narrow PTs
  - o "Other ischaemic heart disease" SMQ: Narrow PTs

# **Suicidality AEs**

Suicidality AE PTs will include the following: completed suicide; suicide attempt; suicidal ideation.

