6.2.5 Sheehan Suicidality Tracking Scale (S-STS)

The S-STS is a prospective clinician administered rating scale that contains questions that track both treatment-emergent suicidal ideation and behaviors ^{17,18}. The S-STS will be completed on a paper form at the site. At the screening visit, the recall period for completing the S-STS is within the last 30 days prior to the screening visit; at all other visits, the recall period for completing the S-STS is since the last visit. Subjects who have a S-STS score of >0 should be evaluated by the Investigator. If the Investigator determines that a subject is at risk of suicide or self-harm,

appropriate measures to ensure the subject's safety and obtain mental health evaluation must be implemented. The subject must immediately be discontinued from the study. The event should be recorded as either an AE or SAE as determined by the Investigator and reported within 24-hours to the Sponsor.

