# 6.5.1.3 On-Treatment AEs by SOC and PT

On-treatment AEs will be summarized by SOC and PT for treated subjects for the following endpoints:

- AEs by severity
- TEAEs by severity
- AEs related to study drug by severity
- SAEs
- AEs leading to study drug discontinuation
- Hepatic-related AEs \*
- Cardiovascular AEs \*
- Suicidality AEs \*.

AEs of special interest are asterisked ("\*").

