# 6.5.7 Safety Narratives

A by-subject listing of safety narrative subject identifiers will be provided for the following select events as columns: all deaths for enrolled subjects; all SAEs for enrolled subjects; all AEs leading to discontinuation of study therapy for treated subjects; on-treatment events of special interest for treated subjects: hepatic-related AEs; cardiovascular AEs; suicidality AEs; AST or ALT > 3 x ULN. The listing will flag subjects with events, as well as display total numbers of subjects with each event and any event in the first row.

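### The suicidality AE list has no term for self-harm or other suicidal behaviour, so such an event would miss the Suicidality AE table and, if non-serious, could miss the narrative listing

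*SAP*

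**What the plan says.** SAP 7.6.1.4 gives the rule for the third category of events of special interest: "Suicidality AE PTs will include the following: completed suicide; suicide attempt; suicidal ideation". It adds no wider query and no catch-all.

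The category is used in two places. SAP 6.5.1.3 sets up the tables: "On-treatment AEs will be summarized by SOC and PT for treated subjects for the following endpoints", and suicidality AEs are one of the three entries marked as of special interest. SAP 6.5.7 makes the same category a narrative trigger: "on-treatment events of special interest for treated subjects: hepatic-related AEs; cardiovascular AEs; suicidality AEs; AST or ALT > 3 x ULN". The narrative listing also has triggers that do not depend on the term list: "all deaths for enrolled subjects; all SAEs for enrolled subjects; all AEs leading to discontinuation of study therapy for treated subjects".

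Protocol 6.2.5 governs what is recorded. A subject scoring above 0 on the S-STS is to be evaluated. The condition for further action is then: "If the Investigator determines that a subject is at risk of suicide or self-harm". In that case safety measures follow, and two statements matter here: "The subject must immediately be discontinued from the study" and "The event should be recorded as either an AE or SAE as determined by the Investigator and reported within 24-hours to the Sponsor".

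**The concern.** The Protocol names self-harm beside suicide as a ground for recording an event, but the SAP category that collects suicidality AEs has no self-harm term. The hepatic and cardiovascular definitions in the same SAP section open with the same kind of stem, so a programmer would read the three terms as the complete rule.

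The purpose of an event-of-special-interest category is to bring the relevant cases together in one table and to prompt a narrative for each. If the list is narrower than the events recorded on this ground, the table can show no suicidality AEs while a relevant case sits elsewhere in the output.

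**Working it through.** No plan figure is involved, so the check is a trace through the outputs. Take an on-treatment AE in a treated subject, recorded after a judgement of self-harm risk and coded to a preferred term outside the three. The coding is an assumption, because neither document gives an example.

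1. **Suicidality AE table (SAP 6.5.1.3).** Membership depends only on the term list. The event is missing whether or not it is serious.
2. **Suicidality narrative trigger (SAP 6.5.7).** It uses the same list, so it does not fire.
3. **Other narrative triggers (SAP 6.5.7).** A fatal event is caught as a death. A serious event is caught as an SAE, and Protocol 8.1.1 counts life-threatening events, hospitalisation and important medical events as serious. This leaves non-serious events.
4. **Discontinuation trigger (SAP 6.5.7).** This refers to discontinuation of study therapy, whereas Protocol 6.2.5 refers to discontinuation from the study. Protocol 4.1 dispenses one single-dose device, and SAP 7.4 defines on-treatment as after the study drug start. By then no study therapy remains to be stopped. Whether a site would record the AE as leading to discontinuation of study therapy is therefore unclear.
5. **General AE outputs.** The event appears in the on-treatment AE tables by severity, SOC and PT (SAP 6.5.1.3) and in the by-subject AE listing (SAP 6.5.1).
6. **S-STS output (SAP 6.5.5).** If the total score is above 0, responses to every question are listed.

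One table therefore misses the event in all cases. The narrative listing may miss it only when it is non-serious and not recorded as leading to discontinuation of study therapy. The general outputs keep it.

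**Size.** Protocol 5.3 excludes subjects with an S-STS score above 0, so the expected count is close to zero and one case matters. Under SAP section 5, about 0.95 × 400 = 380 subjects per group treat a migraine. One case is then 1/380 = 0.26%, shown as 0.3% under the rounding rule in SAP 7.1.2, against a printed 0 if it is missed.

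**The case against.** The strongest reply is that the plan already watches suicidality by another route. The S-STS has its own exploratory objective and its own estimand, and SAP 6.5.5 plans summaries of ideation, behaviour and total scores. The Protocol 6.2.5 process starts from a score above 0, so the cases in question are largely those the S-STS listing is built to show. This stands, and it is why the point is minor. It does not repair the AE table, which is a separate output that will be read by itself. The S-STS route also has a loose end: Protocol 6.2.5 describes a clinician-administered scale, while SAP 6.5.5 summarises self-reported scores.

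A second reply is that the term list is a legitimate choice of scope. The cardiovascular category also picks seven named terms from one query and takes only narrow terms from others, so hand-picked lists are not peculiar to suicidality. That is correct, and the fair contrast is with the hepatic category, which takes a whole query less one stated exclusion. Still, the choice here leaves out something the Protocol names.

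A reader might also infer two stronger things that the documents do not support:

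- *That the Protocol requires self-harm events to be recorded as a category and the SAP contradicts it.* Protocol 6.2.5 is about a judgement that a subject is at risk, and it does not set up a class of self-harm events. The two documents differ in breadth; they do not contradict each other.
- *That self-harm events would get no narrative or would disappear from the report.* Deaths and all SAEs have independent triggers, and every AE remains in the general tables and listings.

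**Conclusion.** The point holds in a narrow form. Followed exactly, SAP 7.6.1.4 leaves an on-treatment event coded outside its three terms out of the Suicidality AE table. A non-serious event of this kind may also get no narrative, depending on how the site records discontinuation.

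This rests on two assumptions: that such an event occurs, which is unlikely given the entry criteria, and that it is coded outside the list, which the documents do not settle. The likely size is one case, changing a cell from 0 to 1. Efficacy results, alpha and sample size are unaffected, as are the general AE tables. Label: cheap improvement.

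**What to change.** Before database lock, amend SAP 7.6.1.4 in two ways:

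- Add preferred terms for suicidal behaviour and self-injury to the suicidality category, either as an explicit list or through a standardised query, as the hepatic category does. The table in 6.5.1.3 and the trigger in 6.5.7 then follow without further edits.
- Have the AEs of subjects with a post-baseline S-STS total above 0 reviewed blinded to treatment, and class as suicidality AEs those recorded because of Protocol 6.2.5. The review is needed because the documents describe no data field linking an AE to that section, so a rule that simply names such AEs could not be programmed.

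The cost is a small term-list update and a short blinded review of what should be very few subjects. The category becomes slightly broader and may take in self-injury without suicidal intent, which a footnote to the table can state. No clinical rule is changed.

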# 7.6.2 Non-Study Medications

Non-study medication imputed start and stop dates will be derived in order to categorize non-study medications as prior or concurrent.

See Section 7.6.1.1 for the definitions of complete dates and partially complete dates.

# 7.6.2.1 Imputed Non-Study Medication Start Dates

To derive the imputed medication start date and numeric imputed start date flag, the following algorithm is used if the reported medication is non-missing:

- 1. If reported start date is complete:
  - o Imputed start date is set to reported start date.
  - o Numeric imputed start date flag is set to 0 (No).
- 2. If reported start date is partially complete:
  - Imputed start date is set to the earliest possible date based on the partial start date information provided.

```
e.g., SEP2018 => 01SEP2018, 2018 => 01JAN2018
```

- Numeric imputed start date flag is set to 1 (Yes).
- 3. If reported start date is not complete and not partially complete then do if informed consent date is complete then do if reported end date is at or before informed consent date then do if birth date is complete then do imputed start date is set to birth date

```
numeric imputed start date flag is set to 1 (Yes)
      else do (i.e., birth date is not complete)
       imputed start date is set to missing
      numeric imputed start date flag is set to 0 (No)
      end
   else if reported end date is after informed consent date then do
      imputed start date is set to informed consent date
     numeric imputed start date flag is set to 1 (Yes)
   end
  end
  else do (i.e., informed consent date is not complete)
   if birth date is complete then do
     imputed start date is set to birth date
     numeric imputed start date flag is set to 1 (Yes)
   end
  else do
   imputed start date is set to missing
   numeric imputed start date flag is set to 0 (No)
  end
 end
end
```

# 7.6.2.2 Imputed Non-Study Medication Stop Dates

To derive the imputed medication stop date and numeric stop date imputed flag, the following algorithm is used if the reported term is non-missing:

- 1. If reported stop date is complete:
  - o Imputed stop date is set to the reported stop date.
  - o Numeric stop date imputed flag is set to 0 (No).
- 2. If reported stop date is partially complete:
  - Imputed stop date is set to the earlier of (a) death date or (b) last possible stop date based on the partial reported stop date information provided.
     e.g., if death date missing, then SEP2013 => 30SEP2013, 2013 => 31DEC2013
  - o Numeric stop date imputed flag is set to 1 (Yes).
- 3. If reported stop date is not complete and not partially complete:
  - o Imputed stop date is set to the earlier of (a) death date or (b) most recent raw database creation date.
  - o Numeric stop date imputed flag is set to 1 (Yes).

## 7.6.2.3 Non-Study Medication Types

Non-study medication types will include prior, previous, current, and concomitant.

Prior medications are defined as those taken before study drug, i.e., imputed start or stop date < study drug start date. These include the following subtypes:

- Previous medications, defined as those taken before informed consent, i.e., those with an imputed start or stop date < informed consent date
- Current medications, defined as those taken on or after informed consent and before study drug, i.e., those with (1) informed consent date ≤ imputed start or stop date < study drug start date or (2) imputed start date ≤ informed consent date < study drug start date 1 ≤ imputed stop date.

Concomitant medications are defined as those taken on or after study drug, i.e., study drug start date  $\leq$  imputed start or stop date.

Listings will display abbreviated medication types. Note that a medication may be classified into multiple types.

# 7.6.3 eDiary Data

# 7.6.3.1 Study Medication

### eDiary Migraine Report

If the subject answered "yes" to taking study medication mistakenly already before using the eDiary, then the eDiary Migraine Report will collect study medication time if the subject reported taking it today or yesterday; otherwise, only the study medication date will be collected.

Otherwise, if the subject answered "no" to taking study medication mistakenly already, had a current pain level of moderate or severe, and answered "yes" to confirming having taken study medication, then the eDiary Migraine Report will record the time the subject has confirmed taking study medication (i.e., finding date/time) as the study medication time.

### eDiary Study Medication Intake Report

Subjects who took study medication without using the eDiary will have the study medication date and time reported by the site on the eDiary Study Medication Intake Report.

# 7.6.3.2 Migraine Characteristics

The following migraine characteristics will be collected at migraine attack onset in the eDiary Migraine Report and post-dose from 15 minutes through 48 hours (e.g., 15, 30, 45, 60, and 90 minutes; 2, 3, 4, 6, 8, 24 and 48 hours) in the eDiary Post-Dose Migraine Report:

- Pain level (none, mild, moderate, severe)
- MBS (nausea, phonophobia, photophobia) in the Migraine Report only
- Nausea status (present, absent)
- Nausea level (none, mild, moderate, severe)
- Phonophobia status (present, absent)
- Phonophobia level (none, mild, moderate, severe)
- Photophobia status (present, absent)
- Photophobia level (none, mild, moderate, severe)
- Functional disability level (normal, mildly impaired, severely impaired, requires bedrest)
- Aura (yes, no) in the Migraine Report only.

The eDiary will allow subjects to report one result per time point per migraine characteristics parameter.

In general, if subjects answered "no" to taking study medication mistakenly already, had current pain level of moderate or severe, and did not use other headache medications, then the eDiary Migraine Report will collect all parameters listed above.

Otherwise, if subjects answered "yes" to taking study medication mistakenly already, then the eDiary Migraine Report will not collect the following parameters: most bothersome symptom, current pain level, nausea status, phonophobia status, and photophobia status. Instead, if the subject provided the time of study medication taken, then the eDiary Migraine Report will collect nausea level, phonophobia level, photophobia level, pain level and functional disability level at the time study drug was taken. Thus, for these subjects at on-study migraine attack onset, a symptom status (nausea, phonophobia, photophobia) of absent is defined as a level of none, and present is defined as a level of mild, moderate, or severe.

Windows for post-dose efficacy measurements (15, 30, 45, 60, 90 minutes; 2, 3, 4, 6, 8, 24, and 48 hours) will be automatically assigned by the eDiary as shown in Table 5.

Table 5: eDiary Automated Efficacy Analysis Windows

Post-Dose Evaluation	Analysis-Specified Interval	Target Time
15 minutes	10 to 20 minutes	Study medication start time + 15 minutes
30 minutes	25 to 35 minutes	Study medication start time + 30 minutes
45 minutes	40 to 50 minutes	Study medication start time + 45 minutes
60 minutes	55 to 65 minutes	Study medication start time + 60 minutes
90 minutes	85 to 95 minutes	Study medication start time + 90 minutes
2 hours	1 hour 45 minutes to 2 hours 15	Study medication start time + 2 hours
3 hours	2 hours 45 minutes to 3 hours 15	Study medication start time + 3 hours
4 hours	3 hours 45 minutes to 4 hours 15	Study medication start time + 4 hours
6 hours	5 hours 45 minutes to 6 hours 15	Study medication start time + 6 hours
8 hours	7 hours 45 minutes to 8 hours 15	Study medication start time + 8 hours
24 hours	23 to 25 hours	Study medication start time + 24 hours
48 hours	47 to 49 hours	Study medication start time + 48 hours
